### **Serious Adverse Event**

Adverse events are classified as serious or non-serious. Serious problems/events can be well defined and include;

- death
- life threatening adverse experience
- hospitalization
- inpatient, new, or prolonged; disability/incapacity
- persistent or significant birth defect/anomaly

and/or per protocol may be problems/events that in the opinion of the sponsor-investigator may have adversely affected the rights, safety, or welfare of the subjects or others, or substantially compromised the research data.

All adverse events that do not meet any of the criteria for serious, should be regarded as **non-serious adverse events**.

### **Adverse Event Reporting Period**

Adverse events will be reported after the subject begins taking the metformin or starts the observation period. The bronchoscopy and surgery are considered standard of care.

### **Preexisting Condition**

A preexisting condition is one that is present at the start of the study. A preexisting condition should be recorded as an adverse event if the frequency, intensity, or the character of the condition worsens during the study period.

### **General Physical Examination Findings**

At screening, any clinically significant abnormality should be recorded as a preexisting condition. At the end of the study, any new clinically significant findings/abnormalities that meet the definition of an adverse event must also be recorded and documented as an adverse event.

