## **6 Study Procedures**

### **6.1 Visit 1**

The subject will be identified by the Thoracic Surgical Clinics. The study coordinator will consent and enroll the subject. The subject will have a blood sample taken for research.

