### **6.3 Visit 3**

At the time of the subjects follow up (less than 90 days from the time of surgery) the subject will be seen by the study team. Eligibility criteria will be assessed and if the subject is still eligible they will be randomized and receive their study treatment (metformin or observation).

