## 7 Statistical Plan

### 7.1 Statistical Methods

All patients meeting the eligibility criteria, and who started treatment, will be considered evaluable for the 2 year RFS rate endpoint. The proportion of 2 year RFS rates (along with the 95% confidence interval) will be estimated within each arm by the number of patients who are recurrence-free and alive at 2 years divided by the total number of evaluable patients in each arm, and compared using a chi-squared test.

Clinical data regarding recurrence-free survival (RFS) will be utilized for development of the metformin sensitivity index. Data collected will be summarized using descriptive statistics, including mean and standard deviation and median and inter quartile range for continuous variables, and using frequencies and percentages for categorical variables. Logistic regression models will be used to assess the impact of metformin sensitivity index metrics, treatment, and the interaction between the metformin sensitivity index metrics and treatment on the 2 year RFS status as the outcome of interest.

Adverse events (AEs) will be compared between metformin and placebo using CTCAE version 4. To evaluate the AE profiles associated with each intervention arm, the maximum grade for each type of AE will be recorded for each participant and frequency tables will be reviewed to determine the overall patterns. The number and severity of AEs (overall and by intervention group) will be tabulated and summarized across all grades. Chi-square tests will be used to compare the AE rates between metformin and placebo.

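### The only adverse-event baseline named is screening, probably before the lung resection, so surgical effects that persist past randomisation can be recorded as treatment-period events

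*Combined protocol and SAP*

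**What the plan says.** Section 8.1 sets the baseline in two places. Under Preexisting Condition: "A preexisting condition is one that is present at the start of the study". Under General Physical Examination Findings: "At screening, any clinically significant abnormality should be recorded as a preexisting condition". A preexisting condition that worsens during the study period is to be recorded as an AE, and so are new clinically significant findings at the end of the study, provided they meet the AE definition.

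The AE window is set separately, under Adverse Event Reporting Period: "Adverse events will be reported after the subject begins taking the metformin or starts the observation period". The next sentence reads "The bronchoscopy and surgery are considered standard of care".

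Section 6 gives the order of events. At Visit 1, "The study coordinator will consent and enroll the subject". Visit 2 is the resection. Visit 3 takes place less than 90 days after surgery, and its content is "Eligibility criteria will be assessed and if the subject is still eligible they will be randomized and receive their study treatment (metformin or observation". No symptom or finding baseline is named there.

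Section 7.1 says that "the maximum grade for each type of AE will be recorded for each participant". AEs are also tabulated overall and by arm, and AE rates are compared with chi-square tests. This serves secondary objective 3.

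**The concern.** On the likeliest reading a lung resection falls between the AE baseline and the start of AE reporting. Pain or breathlessness that began with the operation is absent from the screening record. If it is still there when metformin or observation starts, nothing on file shows that it came before treatment. Breathlessness noted at screening and made worse by surgery fits the worsening rule as written, because the study period is not defined.

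Two things are at stake. The AE rates reported for each arm may include surgical effects, and the pooled comparison between arms loses contrast. Neither can be repaired afterwards if the grades at Visit 3 were never recorded. The treatment is open-label, so a judgement made after allocation about whether a complaint came before treatment is also made knowing the arm.

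**Working it through.** **Timeline (sections 6.1 to 6.3 and 8.1)**

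| Step | Event | AE status |
|---|---|---|
| Visit 1 | Consent, enrolment, blood sample | Likeliest time of screening baseline |
| Visit 2 | Lung resection | Not reported; standard of care |
| Visit 3, <90 days after surgery | Eligibility check, randomisation | Reporting opens when treatment or observation starts; no new baseline |
| End of study | New findings recorded | Only named comparator is screening |

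**Size.** The plan states no AE rate, AE effect size, alpha or power, so it has no figure of its own to reproduce. What follows is a sensitivity range.

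Assumed inputs:
- True any-AE risk p: 45% on metformin, 20% on observation.
- Carry-over s: the share of patients with a persisting surgical effect recorded as an AE. It is the same in both arms and independent of treatment-period events.
- Uncorrected Pearson chi-square test, two-sided 0.05, with exact power by enumerating both binomials.
- 50 per arm (the number to be randomised, section 3.1) and 45 per arm (half of the 90 evaluable for the primary endpoint). The plan states no AE denominator.

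Observed risk = 1 − (1 − s)(1 − p). The observed difference is therefore (1 − s) times the true difference.

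Example at s = 30%:
- metformin: 1 − 0.70 × 0.55 = 61.5%
- observation: 1 − 0.70 × 0.80 = 44.0%
- difference: 0.70 × 25 = 17.5 points

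| s | Metformin | Observation | Difference (points) | Power, 45 per arm | Power, 50 per arm |
|---|---|---|---|---|---|
| 0 | 45.0% | 20.0% | 25.0 | 73.9% | 77.2% |
| 5% | 47.8% | 24.0% | 23.8 | 66.8% | 70.6% |
| 10% | 50.5% | 28.0% | 22.5 | 59.3% | 64.8% |
| 30% | 61.5% | 44.0% | 17.5 | 36.9% | 44.2% |
| 60% | 78.0% | 68.0% | 10.0 | 19.5% | 20.4% |

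**Type I error.** With no drug effect and equal carry-over, both arms share one observed risk. Setting that common risk to each value in the table, the exact rejection rate lies between 4.5% and 5.7%. Equal carry-over dilutes; it does not create false differences.

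**Single AE types.** Section 1.2 says that metformin's side effects are mainly gastrointestinal. For a type that surgery seldom leaves behind, s is near 0. With assumed risks of 40% v 15% at 50 per arm, exact power is 81.9% at s = 0 and 73.9% at s = 5%.

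**A related route that is separate.** Section 6.4 gives monthly AE calls to the metformin arm only; the contact common to both arms is six-monthly (6.5). If 30% of patients carry a surgical effect, the drug has no effect and detection is 90% v 50% (assumed), the observed risks are 27% v 15% and the rejection rate at 50 per arm is 32%. With 90% detection in both arms it is 5%. That bias comes from unequal contact.

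**The case against.** The strongest case is that nothing in the documents says surgical sequelae are to be counted. Section 8.1 defines an AE as an experience associated with use of a medical product, and new end-of-study findings must meet that definition. Calling surgery standard of care, straight after setting the AE start, suggests an intent to keep operative effects out. Screening and the start of the study are never dated against surgery: section 4.3 gives no timing, and 6.1 dates consent and enrolment without using the word screening. The per-type tables keep thoracic complaints apart from gastrointestinal ones, and the comparison is a secondary objective with no stated power target.

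Much of this stands. A reader might infer that sequelae will be counted, or that they will swamp the safety comparison. The documents support neither: the first is one reading of ambiguous rules, and the second needs a high carry-over rate that the documents do not give. A reader might also infer that the gap biases the test, but randomisation after surgery balances the burden in expectation. Nor do the documents say that the metformin AE rate will be used to plan phase III; the Introduction speaks only of feasibility and preliminary data.

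It does not close the gap. The medical-product definition cannot work as a simple causal filter, because the observation arm receives no study product and its AEs are still to be compared. The standard-of-care sentence gives no rule for effects still present when reporting opens. Section 8.2 requires specific questioning at each contact and the recording of all AEs, with follow-up until treatment is judged not the probable cause. Complaints that are not drug-related can therefore enter the record, and 7.1 has no step that removes them.

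**Conclusion.** The concern holds in limited form. No AE baseline is defined at randomisation, so a condition that surgery caused or worsened can be recorded as a treatment-period AE, and its grade at randomisation stays in the maximum-grade summary. The consequence is higher absolute AE rates in both arms and a diluted any-AE comparison; type I error is not inflated when carry-over is equal.

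Under the assumed 45% v 20%, the loss of power at 45 per arm is 7 points at 5% carry-over (74% to 67%), 15 points at 10% (74% to 59%) and 37 points at 30% (74% to 37%). The true carry-over rate is unknown, so the large losses are conditional. For AE types that surgery seldom leaves behind, the effect is small. The point rests on screening preceding surgery, which is the likeliest reading but is not stated. It is worth acting on because the remedy is cheap and the baseline cannot be reliably rebuilt later.

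**What to change.** - **Section 8.1:** define the AE baseline in both arms as Visit 3, before the randomisation envelope is opened, and record there the CTCAE version 4 grade of every existing symptom and finding. Use the same comparator for new findings at the end of the study.
- **Section 7.1:** count an AE only if it is new, or of higher grade than at Visit 3, and tabulate the maximum grade on that basis.

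The cost is a short checklist at an existing visit and a few sentences of protocol text. Taking the baseline before allocation also means that knowledge of the arm cannot influence it. The change does not make AE detection equal between arms: the monthly calls in the metformin arm only (6.4 against 6.5) need their own correction.

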### **Post-study Adverse Event**

All unresolved adverse events should be followed by the sponsor-investigator until the events are resolved, the subject is lost to follow-up, or the adverse event is otherwise explained. At the last scheduled visit, the sponsor-investigator should instruct each subject to report, to the sponsor-investigator, any subsequent event(s) that the subject, or the subject's personal physician, believes might reasonably be related to participation in this study.

### **Hospitalization, Prolonged Hospitalization or Surgery**

Any adverse event that results in hospitalization or prolonged hospitalization should be documented and reported as a serious adverse event unless specifically instructed otherwise in

this protocol. Any condition responsible for surgery should be documented as an adverse event if the condition meets the criteria for an adverse event.

Neither the condition, hospitalization, prolonged hospitalization, nor surgery are reported as an adverse event in the following circumstances:

- Hospitalization or prolonged hospitalization for diagnostic or elective surgical procedures for a preexisting condition. Surgery should **not** be reported as an outcome of an adverse event if the purpose of the surgery was elective or diagnostic and the outcome was uneventful.
- Hospitalization or prolonged hospitalization for therapy of the target disease of the study, unless it is a worsening or increase in frequency of hospital admissions as judged by the clinical investigator.

## **8.2 Recording of Adverse Events**

At each contact with the subject, the study team must seek information on adverse events by specific questioning and, as appropriate, by examination. Information on all adverse events should be recorded immediately in the source document, and also on the appropriate adverse event worksheet. All clearly related signs, symptoms, and abnormal diagnostic, laboratory or procedure results should be recorded in the source document.

All adverse events occurring during the study period must be recorded. The clinical course of each event should be followed until resolution, stabilization, or until it has been ultimately determined that the study treatment or participation is not the probable cause. Serious adverse events that are still ongoing at the end of the study period must be followed up, to determine the final outcome. Any serious adverse event that occurs after the study period and is considered to be at least possibly related to the study treatment or study participation should be recorded and reported immediately.

## **8.3 Reporting of Serious Adverse Events and Unanticipated Problems**

When an adverse event has been identified, the study team will take appropriate action necessary to protect the study participant and then complete the Study Adverse Event Worksheet and log. The sponsor-investigator will evaluate the event and determine the necessary follow-up and reporting required.

### **8.3.1 Sponsor-Investigator reporting: notifying the Mayo IRB**

The sponsor-investigator will report to the Mayo IRB any UPIRTSOs and NonUPIRTSOs according to the Mayo IRB Policy and Procedures.

## **8.4 Medical Monitoring**

It is the responsibility of the Principal Investigator to oversee the safety of the study at his/her site. This safety monitoring will include careful assessment and appropriate reporting of adverse events as noted above, as well as the construction and implementation of a site data and safety-monitoring plan (see section 10 “Study Monitoring, Auditing, and Inspecting”). Medical monitoring will include a regular assessment of the number and type of serious adverse events.

## 9 Data Handling and Record Keeping

### 9.1 Confidentiality

Information about study subjects will be kept confidential and managed according to the requirements of the Health Insurance Portability and Accountability Act of 1996 (HIPAA). Those regulations require a signed subject authorization informing the subject of the following:

- What protected health information (PHI) will be collected from subjects in this study
- Who will have access to that information and why
- Who will use or disclose that information
- The rights of a research subject to revoke their authorization for use of their PHI.

In the event that a subject revokes authorization to collect or use PHI, the investigator, by regulation, retains the ability to use all information collected prior to the revocation of subject authorization. For subjects that have revoked authorization to collect or use PHI, attempts should be made to obtain permission to collect at least vital status (long term survival status that the subject is alive) at the end of their scheduled study period.

### 9.2 Source Documents

Source data is all information, original records of clinical findings, observations, or other activities in a clinical trial necessary for the reconstruction and evaluation of the trial. Source data are contained in source documents. Examples of these original documents, and data records include: hospital records, clinical and office charts, laboratory notes, memoranda, subjects' diaries or evaluation checklists, pharmacy dispensing records, recorded data from automated instruments, copies or transcriptions certified after verification as being accurate and complete, microfiches, photographic negatives, microfilm or magnetic media, x-rays, subject files, and records kept at the pharmacy, at the laboratories, and at medico-technical departments involved in the clinical trial.

### 9.3 Case Report Forms

The study case report form (CRF) is the primary data collection instrument for the study. All data requested on the CRF must be recorded. All missing data must be explained. If a space on the CRF is left blank because the procedure was not done or the question was not asked, write "N/D". If the item is not applicable to the individual case, write "N/A". All entries should be printed legibly in black ink. If any entry error has been made, to correct such an error, draw a single straight line through the incorrect entry and enter the correct data above it. All such changes must be initialed and dated. Do not erase or use "white-out" for errors. For clarification of illegible or uncertain entries, print the clarification above the item, then initial and date it. If the reason for the correction is not clear or needs additional explanation, neatly include the details to justify the correction.

### 9.4 Records Retention

The sponsor-investigator will maintain records and essential documents related to the conduct of the study. These will include subject case histories and regulatory documents as outlined in the Mayo Clinic Research Policy Manual –“Access to and Retention of Research Data Policy.”

## **10 Study Monitoring, Auditing, and Inspecting**

### **10.1 Study Monitoring Plan**

The investigator will allocate adequate time for such monitoring activities. The Investigator will also ensure that the monitor or other compliance or quality assurance reviewer is given access to all the study-related documents and study related facilities (e.g. pharmacy, diagnostic laboratory, etc.), and has adequate space to conduct the monitoring visit.

### **10.2 Auditing and Inspecting**

The investigator will permit study-related monitoring, audits, and inspections by the IRB, the sponsor, and government regulatory agencies, of all study related documents (e.g. source documents, regulatory documents, data collection instruments, study data etc.). The investigator will ensure the capability for inspections of applicable study-related facilities (e.g. pharmacy, diagnostic laboratory, etc.).

Participation as an investigator in this study implies acceptance of potential inspection by government regulatory authorities and applicable compliance offices.

## **11 Ethical Considerations**

This study is to be conducted according to United States government regulations and Institutional research policies and procedures.

This protocol and any amendments will be submitted to a properly constituted local Institutional Review Board (IRB), in agreement with local legal prescriptions, for formal approval of the study. The decision of the IRB concerning the conduct of the study will be made in writing to the sponsor-investigator before commencement of this study.

All subjects for this study will be provided a consent form describing this study and providing sufficient information for subjects to make an informed decision about their participation in this study. This consent form will be submitted with the protocol for review and approval by the IRB for the study. The formal consent of a subject, using the Approved IRB consent form, must be obtained before that subject undergoes any study procedure. The consent form must be signed by the subject or the subject's legally authorized representative, and the individual obtaining the informed consent.

## **12 Study Finances**

### **12.1 Funding Source**

This study is financed through a grant from the Alliance for Clinical Trials in Oncology.

### **12.2 Conflict of Interest**

Any study team member who has a conflict of interest with this study (patent ownership, royalties, or financial gain greater than the minimum allowable by their institution, etc.) must have the conflict reviewed by a properly constituted Conflict of Interest Committee with a Committee-sanctioned conflict management plan that has been reviewed and approved by the study sponsor-investigator prior to participation in this study.

